The cluster component reflects the fact that treatment will be randomized to sites rather than patients. The cohort component reflects the fact that patients will be recruited from ongoing longitudinal cohorts via web-based interactions to determine eligibility. This aspect is a variant of the cohort multiple randomized controlled trial but in which only one trial will be performed (as opposed to multiple trials)²³.

In brief, SSc patients in the International Systemic Sclerosis Inception Cohort (INSYNC) sites, of which all participants in this trial will belong, are seen for study purposes on a yearly basis, to complete detailed, standardized protocols. Data are entered into databases and subsequently harmonized across all INSYNC sites. Although the initial purpose of INSYNC was to pursue research on inception cases, (defined as < 2 years disease duration), all INSYNC sites collect data on prevalent cases as well. Thus, for the purposes of this study, all patients seen, regardless of disease duration, will be assessed at a yearly visit to see if they are able to, and will consent to, accessing a web based Gastrointestinal Symptom Score (GSS) questionnaire that they will fill out at home at regular 3 month intervals. These questionnaires will both determine their eligibility for the SIBO study and will be the major outcome measure. Before the study begins, individual sites, which will total about 30 around the world, will be randomly assigned to be treatment protocol or standard of care arms. Every 2 weeks the study coordinator will have access to the patient questionnaire results. As soon as an eligible case is detected, ie a score of ≥ 5 on the GSS, the site will be notified of this patient.

Protocol treatment sites will be expected to see the patient within a pre-specified window of time. The doctors at that site will apply the treatment algorithm and will make decisions about response to treatment based on the algorithm and on specific patient answers to questionnaires. The treatment protocol will only be made available to IRBs, not to any site personnel before randomization. This was derived from a survey of rheumatologists in many countries and gastroenterologists, mostly in North America, who were asked multiple questions about how they would treat and follow up patients with suspected SIBO. (Appendix 1- Survey of Experts)

The algorithm created for this data represents the best consensus of those opinions.

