For the target for “success” we will use the GSS questionnaire which will be administered on paper when the patient visits the doctor’s office for follow-up. In the study validating the GSS in SSc-associated SIBO, patients in whom the breath tests became negative after treatment had a significantly lower total GSS score than those with SIBO who did not become breath test

Pragmatic, multicentre, cluster, cohort randomised controlled treat-to-target trial for treatment of small intestinal bacterial overgrowth in systemic sclerosis (SSc) – A Pilot Project

negative (mean (range) 1.5 (0–9) vs. 8 (5–23), $p=0.001$)^{10,24}. None of the patients with eradication of SIBO had diarrhea. Hence, “no diarrhea plus a total GSS of < 5” will be the treatment target.

Meanwhile, those physicians randomly assigned to standard of care will also be informed of their patients who met eligibility criteria. They will not be aware of the detailed treatment protocol but will be informed of which medications are in the protocol eg antibiotics, prokinetics etc. They will be free to contact the patients at their convenience and to treat them in any way they deem suitable, preferably using these medications but at doses and frequencies according to their own wishes. As symptoms of SIBO tend to recur after short courses of treatment, and as the treatment protocol will be designed to adapt to this, we will follow each patient for one year from the time their physician was notified that they were eligible for the study. The primary outcome of the trial will be based on the patient reported outcomes regarding symptoms over the entire year.

What are the proposed primary and secondary outcome measures of the main trial?

Primary: The primary outcome is the total GSS score.

Secondary: Secondary outcomes include all GSS subscales. HRQoL will be assessed by the social scale of the UCLA GIT 2.0 and the NIH Promis29. Hospitalization for SIBO will be recorded during the 2 year study.

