What are the known safety concerns of the treatment(s), and are the concerns different for the proposed repurposed indication? This study will investigate the use of antibiotics and possibly other medications (eg. promotility, bile sequestrants, anti-diarrheals) for SSc SIBO treatment. For all antibiotics, hypersensitivity reactions such as exfoliative dermatitis, rash, urticaria, flushing, angioneurotic edema, pruritus, and anaphylaxis are a concern. Prolonged use may result in fungal or bacterial super-infection, including *C. difficile*-associated diarrhea and pseudomembranous colitis. Cholestyramine resin, which may be one of the drugs selected for use, should be used with caution in patients with triglyceride levels 250-299 mg/dL. Chronic use may be associated with bleeding problems (especially in high doses. Cholestyramine (especially high doses or long-term therapy) may decrease the absorption of folic acid, calcium, fat-soluble vitamins (vitamins A, D, E, and K), and iron. However, antibiotics and drugs such as cholestyramine are already in use for SIBO, although not in a standardized fashion, so the risks are not increased in this proposal. The use of certain promotility drugs is associated with a prolonged QT interval.

THE PILOT PROJECT

Objectives: To determine the feasibility of the full project. This will be a trial with 3 months of recruitment and 6 months of follow up for each case.

Specific Aims:

1. Determine if ethics committees perceive any major issues regarding the ultimate trial
2. Determine if the sites are approaching all eligible patients with study and offering consent forms.
3. Determine the signing rate of consent.
4. Determine patient adherence to web access for questionnaires.

Pragmatic, multicentre, cluster, cohort randomised controlled treat-to-target trial for treatment of small intestinal bacterial overgrowth in systemic sclerosis (SSc) – A Pilot Project

5. Assess our method for detecting eligible cases from web questionnaires.
6. Assess whether physician notifications are being sent out quickly after detecting eligible cases.
7. Assess the timeliness and completeness of physician receipt of notification of patient eligibility.
8. Assess physician adherence to treatment protocol:
 - a. how soon protocol patients are brought in to see doctor after receipt of notice.
 - b. does doctor record what he does accurately.
 - c. does he/she schedule return visits according to protocol.

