Website Questionnaires: Subjects will access and fill in the GSS questionnaire which will be used both for screening for SIBO and for assessment of improvement with treatment. If the score of the GSS is ≥ 5 then the UCLA GIT and PROMIS GI questionnaires will also be triggered. (Appendix 4 – Questionnaires) They will be sent the link to the questionnaires via email from the central study coordinator. In this pilot, we will only screen subjects for 3 months total so the questionnaires will be filled in once a month for those 3 months. This will allow us to better assess the use of the website over a short period of time. Subjects will be notified immediately after consent is signed and thereafter once a month by email that they should fill in the questionnaire. A link will be provided. If the questionnaire is not filled out within 5 days an automatic repeat email will be sent out. We will repeat this every 5 days for a total of 3

Pragmatic, multicentre, cluster, cohort randomised controlled treat-to-target trial for treatment of small intestinal bacterial overgrowth in systemic sclerosis (SSc) – A Pilot Project

additional reminders. If there is no response after that the site coordinator will be informed and asked to phone the subject to determine and record the reason for the non-response and if the subject no longer wishes to be in the study they will be withdrawn.

Notification of Doctor of Eligible Case: If a score on the GSS is ≥ 5 , the computer will send an automatic notice to the office of the doctor and to the doctor him/herself telling them of this. The email notification will be repeated in 5 days to be sure that it has not been missed, and the provider will be asked to verify that it was received.

First Appointments: Upon receipt of the notice, the protocol doctors will be expected to make an appointment within the timeframe outline in the protocol. Standard care doctors, who will not know the details of this protocol, will decide on their own if and when to see the patient. Upon receipt of this notice the secretaries or clerks at the site will be asked to insert a treatment sheet (Appendix 5 – Treatment Sheet) in the doctor's chart. This sheet will be used to assess the timeliness of the first visit after notification, about the adherence of protocol doctors to protocol treatment and the types of medications and general pattern of treatment of the standard of care doctors.

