Subsequent Appointments: The timing of subsequent appointments will be left to the discretion of the doctors but the protocol doctors will be expected to adhere to the protocol for follow up frequency and intervals. The treatment sheets will assess adherence. At each protocol visit the patient will fill out the GSS in the office as the doctor will use the score to determine success of treatment rather than relying simply on history. This is outlined in detail in the treatment protocol.

Recruitment and follow-up period: Patients will be recruited over a period of 3 months and followed up for 6 months. The total duration of the study will thus be 9 months. However, the protocol doctors will be asked to try to continue to adhere to the protocol. If there are no major changes in the protocol based on this pilot, all the patients enrolled in these 3 months may be rolled into the larger full study. This will be decided after the pilot data has been fully assessed.

Safety Monitoring: The treatment sheets will have fields to record any suspected side effects of treatment and the physicians will record this. A Data Monitoring and Safety Board (DSMB) will be established before the start of the pilot. We will request that a copy of all treatment sheets be faxed or emailed to the coordinating site after each visit. These will be forwarded to the DSMB members. If any member detects a serious side effect that they feel should lead to a change in protocol an immediate teleconference of the DSMB will be arranged.

Chart Audit: To determine if there is a disagreement between the treatment questionnaires and what the doctors actually did, we will perform a chart audit of a sample of charts. Permission to do this will be included in the consent forms. We will audit 30 % of charts randomly selected from each doctor. The audits will be of all relevant visits over the study period. We will ask to have the relevant pages from these charts faxed to us. We will find non-English speaking volunteers from the translation service at the central coordinating hospital to help fill out data extraction forms (Appendix 6 – Data Extraction Sheet) for the chart review of non-English speaking centers. The study coordinator will perform the audit.

Data Analyses: Each of the aims will be assessed. Statistics will be essentially descriptive. The success of the pilot will not depend on one global assessment. As individual elements of the

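### The pilot schedules the home symptom score only for the three screening months, so notified patients have no scheduled web score for roughly the last 3 to 6 months of follow-up

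*Protocol*

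**What the plan says.** **Pilot timetable.** Under Website Questionnaires, the web GSS is described as one "which will be used both for screening for SIBO and for assessment of improvement with treatment". The only explicit timetable follows in that paragraph: "we will only screen subjects for 3 months total so the questionnaires will be filled in once a month for those 3 months". The stated reason is that a short period lets the team judge how the website is used.

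**Pilot follow-up.** The Objectives read: "This will be a trial with 3 months of recruitment and 6 months of follow up for each case". Recruitment and follow-up period gives the same durations and a total of 9 months. It adds that, if the protocol does not change much, "all the patients enrolled in these 3 months may be rolled into the larger full study". That decision waits until the pilot data have been assessed. Under Sites, the pilot sites keep their arm for the full study.

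**Full trial.** Patients complete at home a GSS "questionnaire that they will fill out at home at regular 3 month intervals", and "These questionnaires will both determine their eligibility for the SIBO study and will be the major outcome measure". On duration: "we will follow each patient for one year from the time their physician was notified that they were eligible for the study". On the outcome: "The primary outcome of the trial will be based on the patient reported outcomes regarding symptoms over the entire year".

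**Office GSS.** A paper GSS is completed at visits in the protocol arm to steer treatment (Subsequent Appointments). None is specified for standard-care patients, whose doctors choose whether and when to see them (First Appointments).

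**The concern.** The web GSS has two purposes in the pilot, but the timetable is derived from only one of them. It stops when screening stops. The second purpose, judging improvement, has no time point after that, although each notified patient is followed for 6 months.

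Two things are at stake.

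- **Feasibility.** The pilot exists to show that the full trial can be run, and the full trial depends on notified patients returning the home GSS for a year. Aim 4 sets a month-to-month retention target of at least 80%. On the stated timetable it can be measured only inside the three screening months, and it does not separate notified patients from the rest.
- **Roll-in.** Because that decision comes after the pilot, any scores not collected by then cannot be recovered. Notified patients who are rolled in could enter the arm comparison with part of their outcome year missing.

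**Working it through.** **Inputs from the protocol.** Recruitment 3 months; follow-up 6 months per case; web forms monthly for 3 months, the first sent straight after consent; full-trial home GSS every 3 months for one year from notification; about 25% of patients expected to reach a score of 5 or more (Data Analyses, aim 5). The total reproduces: 3 + 6 = 9 months.

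**Step 1: time without a scheduled web GSS.** Count follow-up from notification. Then gap = 6 − (time of last web form − time of notification). The text allows three readings of the 3-month limit:

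| Reading | Web forms after notification | Gap (months) |
|---|---|---|
| Own consent, forms at months 0, 1, 2 | 0 to 2 | 4 to 6 |
| Own consent, forms at months 0, 1, 2, 3 | 0 to 3 | 3 to 6 |
| Everyone stops at pilot month 3 | 0 to 3 | 3 to 6 |

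For example, a patient notified on the first form with a last form at month 3 has a gap of 6 − 3 = 3. A patient notified on the last form has 6 − 0 = 6. If the 6 months run from consent instead, the gap is 6 − 2 = 4 or 6 − 3 = 3. A score 6 months after notification is scheduled under none of the readings. A score at 3 months is scheduled only if the patient is notified on the first form and a month-3 form exists.

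**Step 2: what aim 4 can see.** Forms at months 0, 1 and 2 give two month-to-month transitions. No transition is observed in the later months of follow-up.

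**Step 3: scores lost on roll-in.** This step needs three assumptions that the protocol does not supply: the outcome year starts at the pilot notification date, quarterly scores fall due 3, 6, 9 and 12 months after it, and web collection restarts at pilot month R.

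Take forms at months 0, 1 and 2 after consent at time c, with c between 0 and 3. Notification is at n = c, c + 1 or c + 2, so n lies between 0 and 5. The last form is at most 2 months after n, so no quarterly score is caught in screening. The number lost is the number of n + 3, n + 6, n + 9, n + 12 that fall before R:

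| Assumed restart R | n below 3 | n from 3 to 5 |
|---|---|---|
| Month 9 | n + 3, n + 6: 2 lost | n + 3: 1 lost |
| Month 12 | 3 lost | 2 lost |
| Month 15 | 4 lost | 3 lost |

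If everyone stops at pilot month 3, the ranges are the same: 1 to 2, 2 to 3 and 3 to 4. If a month-3 form is added on the own-consent reading, they become 0 to 2, 1 to 3 and 2 to 4. The 0 arises only for a patient recruited on the last day.

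**Step 4: who is affected.** Notified patients only: about 25 per 100 on the protocol's expectation, or 19/51 = 37 per 100 in the cited series, which counts scores above 5. The other 63 to 75 per 100 have no outcome year running and lose nothing.

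**The case against.** **The text never says that collection stops.** The quoted sentence can be read as limiting screening and explaining why forms are monthly. The Consent and Patient Recruitment section and the Website Questionnaires section both mention monthly forms with no end date, and Methods says the pilot mirrors the full trial. Aim 4 speaks of each later questionnaire without a cap. This stands in part: the intention may well be to continue. But the one sentence with a duration ties the forms to the three screening months, and none of the other passages names a later time point. The treatment protocol and appendices are not shown and might supply one.

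**No pilot result depends on it.** The nine aims concern feasibility, the analysis is descriptive, and none uses a GSS taken after treatment. This stands in full. A reader might infer that the pilot's own findings are compromised; they are not.

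**Roll-in is uncertain.** It is optional, depends on few protocol changes, and no start date for the outcome year is given for rolled-in patients. The full trial could screen them again or start a new year. This also stands, which is why the score counts are conditional.

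**Bias between arms.** A reader might infer that the gap favours one arm, since an office GSS is specified only for protocol visits. The documents do not support that. The web score is missing in both arms alike, and the full-trial overview makes the home questionnaire the outcome and the office form the treatment target. Bias would need office scores to be substituted for web scores, which nothing in the protocol proposes.

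**Conclusion.** The point holds as a gap in the data collection schedule. The only explicit pilot timetable for the web GSS ends with screening, which leaves roughly the last 3 to 6 months of follow-up without a scheduled web score in either arm. That conclusion rests on the protocol text alone.

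The firm consequence is for feasibility: the pilot does not show whether notified patients go on supplying the full trial's primary outcome. The consequence for roll-in is conditional. If the pilot notification date starts the outcome year, part of that year's home GSS is missing in both arms and cannot be recovered. The amount is about 1 to 2 of 4 quarterly scores with forms at months 0, 1 and 2 and a month-9 restart, and more with a later one. Patients notified early would have up to 2 or 3 monthly scores inside the screening window, so their first months are not blank.

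**What to change.** In Website Questionnaires, apply the 3-month limit only to the screening of patients who have not been notified. Keep sending the web GSS to every notified patient, at protocol and standard-care sites alike, to the end of the 6-month follow-up: monthly, or at least 3 and 6 months after notification. Then send it quarterly until roll-in is decided. Report the retention of notified patients under aim 4.

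If the sponsor prefers not to extend collection, state that patients notified in the pilot will not enter the full trial's primary analysis. That loses them from that analysis.

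**Cost.** A sentence or two in the protocol and matching consent wording. The website and automatic emails are already planned. To 6 months after notification, each notified patient answers at most 2 quarterly or 6 monthly forms, less any already answered during screening. Non-responders bring further reminders and possibly a call from the site. The quarterly forms after that have no fixed end, because the protocol sets no date for the roll-in decision.

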 - d. does he/she use in office questionnaires for treat to target.
 - e. does he/she base decisions on these questionnaires.
 - f. does he/she follow algorithm sequentially.
9. For control sites,
 - a. Record how soon protocol patients are brought in to see doctor after receipt of notice.
 - b. Assess whether the doctor accurately records what he/she does.

Methods: The pilot project will reproduce the full trial but at only 10 sites, 5 standard care and 5 treatment protocol.

Sites: We will choose 2 sites in Australia, 2 in the Netherlands, 2 in Canada, 2 in Spain and 2 in Germany. In each country one site will be randomly selected to be a protocol site and one standard care site. If a PI on the grant comes from a site, then another rheumatologist unaware of the treatment protocol will act as the treating physician. Sites in INSYNC are located in Australia, Canada, the U.S., the Netherlands, Spain, Germany and Sweden. This selection will give us representation from English and non-English speaking centers and from an array of countries with different medical cultures. It will also test our ability to monitor sites far from the study center in Montreal.

For the full study, these sites will retain their treatment status as assigned for this pilot.

The inclusion criteria for a site is that they agree in writing to adhere to the overall study protocol, and specifically that they agree, before seeing the treatment algorithm and before being assigned to protocol or standard care, to accept to treat according to the algorithm if they are assigned to that.

Patient Inclusion /Exclusion: Every patient who visits the participating doctor at a site over the recruitment period will be approached for consent to participate in the trial.

Inclusion: The patient must have an email address and must be computer literate enough to fill out the online questionnaires. From our experience where patients are asked if they have emails to see if they can participate, about 70% do. The online questionnaires will be available in the language of all countries participating.

Exclusions:

Pragmatic, multicentre, cluster, cohort randomised controlled treat-to-target trial for treatment of small intestinal bacterial overgrowth in systemic sclerosis (SSc) – A Pilot Project

- patients with allergies to any of the drugs in the protocol which cannot be substituted for another protocol drug, and this will apply to standard care patients as well.

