- patients with concomitant severe disease that would make it unlikely that they will survive for one year;
- patients with other illness or use of substances known to cause diarrhea;
- history of antibiotics in the 12 weeks prior to inclusion;
- history of intestinal pseudo-obstruction;
- inability to complete the symptom questionnaires;
- no functional level of written & spoken languages;
- previous *C. Difficile* infection;
- previous gastrointestinal surgery;
- prolonged QT interval;
- pregnancy or breastfeeding.

Screening for exclusions will be done at the site before the patient is consented. (Appendix 2- Exclusion Criteria Questionnaire)

As is typical of a pragmatic trial, we will keep inclusions broad and exclusions narrow.

Patients already on prokinetics will not be excluded but that prokinetic will be considered a failed drug and the treatment algorithm will proceed as such.

Consent and Patient Recruitment: Patients will be recruited at their regular yearly visit to their INSYNC physician or to any other participating physician. The study will be explained and they will be asked to sign a consent, (Appendix 3 – Consent Form), which will ask for their consent to be contacted by email. The email will contain a link to a website where they will be asked to fill in 2 forms, the UCLA GIT 2.0 and the GSS, on a monthly basis. They will be explained that their site will be using a specific treatment protocol or standard care and that the treatment protocol will employ much the same drugs that most physicians use for the problem of SIBO but in a very defined way. They will get a call or notice to see their doctor if they have evidence of SIBO based on their GSS test scores no matter what type of site they are assigned to.

Once a patient signs a consent, the global study coordinator will be informed that the patient is in the study via email. The email will include the patient's local study ID and their email address.

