Pragmatic, multicentre, cluster, cohort randomised controlled treat-to-target trial for treatment of small intestinal bacterial overgrowth in systemic sclerosis (SSc) – A Pilot Project

study can each be addressed separately, by making changes to specific parts of the protocol, the success of each element will be as follows:

1. Determine if ethics committees perceive any major issues regarding the ultimate trial.

Success: There will be 10 sites and thus 10 ethics committee responses. Success will be **NO** substantive suggested changes to the protocol.

If Not Successful: **Any** suggestion for a change will be addressed for full trial.

2. Determine if the sites are approaching all yearly INSYNC patients with study and offering consent forms at the time of the visit.

Success: $\geq 80\%$ of yearly INSYNC patients are offered the consent.

If Not Successful: Interview the local research assistants or nurses and see if there seems to be a systemic issue that could be addressed to improve the frequency with which patients are approached.

3. Determine the signing rate of consent within 1 week of the time of the visit.

Success: $\geq 80\%$ acceptance rate by patients.

If Not Successful: Interview the local research assistants or nurses and see if there seems to be a systemic issue that could be addressed to improve the acceptance rate.

4. Determine patient adherence to web access for questionnaires.

Success: $\geq 70\%$ of patients go to website and answer first set of questionnaires. $\geq 90\%$ of those who answer do so within 10 days. For those who do answer first questionnaire, consider them as successes and study participants. For these subjects, do similar assessments for each subsequent questionnaire. Successful retention will be $\geq 80\%$ of those who answered each month will do so at following month.

If Not Successful: We will consider changes to the wording and frequency of reminders.

5. Assess our method for detecting eligible cases from web questionnaires.

Success: We expect that about 25% of cases will show SIBO positive responses (score ≥ 5 on GSS) to the questionnaires at some point over 3 months. In the study of 51 unselected patients with SSc, 22 (43.1%) patients were identified who fulfilled the breath test criteria of SIBO¹⁰. The sensitivity and specificity of GSS of digestive symptoms >5 to predict SIBO 0.909 and 0.862, respectively. In the 51 cases, 19 patients (37%) has scores > 5 .

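### Aim 2 is stated over eligible patients but scored over all yearly INSYNC patients, so a miss on the 80% bars of Aims 2 and 3 may reflect inability to join and not poor approach or refusal

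*Protocol*

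**What the plan says.** The approach aim appears twice, over two populations. Under The Pilot Project, Specific Aims item 2 reads "Determine if the sites are approaching all eligible patients with study and offering consent forms". Data Analyses item 2 reads "Determine if the sites are approaching all yearly INSYNC patients with study and offering consent forms at the time of the visit", and success is at least 80% "of yearly INSYNC patients are offered the consent".

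Data Analyses item 3 sets a second bar: at least 80% acceptance, with signatures counted within one week of the visit. It does not say over which patients.

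Three other statements bear on who can be offered the form and who can sign it:

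- Patient Inclusion/Exclusion: "The patient must have an email address and must be computer literate enough to fill out the online questionnaires". On how many can: "From our experience where patients are asked if they have emails to see if they can participate, about 70% do".
- End of the exclusion list: "Screening for exclusions will be done at the site before the patient is consented". The list includes being unable to complete the symptom questionnaires.
- Patient Inclusion/Exclusion, on who is approached: "Every patient who visits the participating doctor at a site over the recruitment period will be approached for consent to participate in the trial". The overview of the full project is similar: "all patients seen, regardless of disease duration, will be assessed at a yearly visit to see if they are able to" use the web questionnaire, and will consent to doing so.

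Consent and Patient Recruitment also recruits through participating physicians other than the patient's INSYNC physician, a source that the Aim 2 denominator does not name.

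**The concern.** Eligible patients and yearly INSYNC patients are not the same group. On the protocol's own figure, about 30 in 100 attending patients lack e-mail and cannot join. Whether they enter the denominator, and whether a patient screened out before consent counts as offered, decides whether a well-run site can reach 80%.

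The pilot exists to tell the investigators which parts of the full trial need changing. The listed response to a miss on either item is to interview local staff about how often patients are approached or how often they accept. If the true reason is that patients have no e-mail, that response starts from the wrong question. Sites that read the rule differently would also report rates that cannot be compared.

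**Working it through.** Both 80% thresholds are set and not derived, so there is no figure to reproduce. The check is the highest value that each rate can take.

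**Inputs from the protocol.** E-mail share *m* = 0.70 (Patient Inclusion/Exclusion); bars of 0.80 for Aims 2 and 3 (Data Analyses, items 2 and 3).

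**Assumed.** Share *x* of e-mail holders removed by the other exclusions: 0 in the base case, 10% as an illustration. The protocol gives no figure. The share able to join is *e* = *m*(1 − *x*).

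**Step 1: each rate alone, per 100 attending patients, *x* = 0.**

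| Site practice | Aim 2 maximum | Aim 3 maximum, over all offered | Aim 3 maximum, over those able to join |
|---|---|---|---|
| Form offered only to those able to join | 70/100 = 70% | 70/70 = 100% | 70/70 = 100% |
| Form offered to every visitor | 100/100 = 100% | 70/100 = 70% | 70/70 = 100% |

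Each practice can cap one of the two rates, and the second does so only on one choice of base.

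**Step 2: the same result, two scores.** With universal offers, 56 signatures are 56/70 = 80% of those able to join (pass) and 56/100 = 56% of those offered (miss).

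**Step 3: both bars together, with Aim 2 over yearly patients and Aim 3 over those offered.** Let *f* be the share offered.

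- Aim 2 needs *f* ≥ 0.80.
- Aim 3 needs signatures of at least 0.80*f*. Signatures cannot exceed *e*, so *f* ≤ *e*/0.80 = 0.70/0.80 = 0.875.
- At the lowest permitted *f*, signatures must reach 0.80 × 0.80 = 0.64 of yearly patients, which is 0.64/0.70 = 91.4% of all e-mail holders. At *f* = 0.875 it is 0.70/0.70 = 100%.
- With *x* = 10%, *e* = 0.70 × 0.90 = 0.63 and the requirement is 0.64/0.63 = 101.6%, which is impossible.

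**Step 4: sensitivity to the 70%.** Over an assumed e-mail share of 60% to 85%, the cap in Step 1 is 60% to 85%. It stops ruling out a pass once *e* ≥ 0.80. With *x* = 10% that needs an e-mail share of 0.80/0.90 = 88.9%.

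**Step 5: sampling variation.** The cap refers to the underlying share. If the true rate is 70%, the binomial chance of observing 80% or more is 7.9%, 1.6% and 0.09% with 50, 100 and 200 patients. These numbers are assumed, as the pilot's size is not stated.

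**Step 6: does the rule under fix still detect poor approach?** Take a site that screens all 100 patients and a site that misses 25 at random.

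| Rule | All screened | 25 missed |
|---|---|---|
| Current Aim 2, offers only to those able to join | 70/100 = 70% (miss) | 75 × 0.70/100 = 52.5% (miss) |
| Aim 2 as under fix | (70 + 30)/100 = 100% (pass) | 75/100 = 75% (miss) |

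The current rule fails both sites. The reworded rule separates them.

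**The case against.** The strongest reply is that the protocol tells sites to approach every visiting patient. Scoring offers over all yearly INSYNC patients fits that instruction, and the sentence on exclusions places screening before consent, not before the offer. On that reading Aim 2 can be met. This stands. A reader might infer that the Aim 2 bar is out of reach as written, and the documents do not support that: it is out of reach only if sites hold the form back from patients who cannot join, which the text neither requires nor rules out.

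Three further points carry weight.

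- Elsewhere in the Specific Aims, eligible means a symptom score of 5 or more, which is not known at the consent visit. The word in item 2 may be loose, and Data Analyses may be meant as the working definition. That softens the contradiction but does not remove it, nor does it say how a screened-out patient is scored.
- An acceptance rate would ordinarily leave out people who are not allowed to accept. That may well be intended. Taken alone, the missing base in Aim 3 is a detail that an analysis plan could supply. It matters here because it decides where the e-mail limit falls once every visitor is offered the form.
- The two caps do not arise from the same practice. With universal offers, and acceptance counted among those able to join, neither rate is capped. It would therefore be wrong to infer that the two criteria are incompatible. They conflict only on the bases in Step 3, and even there a narrow window remains before other exclusions.

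Staff interviews after a miss might also bring the e-mail problem to light.

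**Conclusion.** The point holds as a minor inconsistency in two feasibility criteria. Aim 2 names one population and is scored over another. Depending on how sites offer the form and how acceptance is counted, one of the two 80% bars can be held at about 70% by lack of e-mail alone. On the least favourable pair of bases, a pass on both needs 80% to 87.5% of yearly patients offered and at least 91.4% of e-mail holders signing, with no other exclusion at work.

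This rests on the protocol's approximate 70%. The cap no longer rules out a pass once at least 80% of attending patients are able to join. The 10% exclusion share, the 60% to 85% range and the patient numbers in the working are illustrations.

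A reader might infer that the pilot's overall result or the full trial's design turns on this. The documents do not support that: the statistics are descriptive, success does not rest on one global assessment, a miss on these items leads only to staff interviews, and no test, stop/go rule or sample size depends on them. What is affected is whether a miss can be read as poor approach or refusal.

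**What to change.** Keep both 80% thresholds and state one denominator for each:

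- **Aim 2:** patients offered consent, or screened and documented as ineligible, divided by all patients attending a yearly visit with a participating physician in the recruitment period. Patients not screened then count as not approached.
- **Aim 3:** patients who sign within one week of the visit, divided by eligible patients offered consent.
- **Report separately** the share without e-mail or computer literacy and the share with an exclusion.
- **Align the wording** of Specific Aims item 2, Patient Inclusion/Exclusion, Consent and Patient Recruitment, and Data Analyses items 2 and 3.

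The cost is two reworded criteria and one screening-log line per attending patient: offered; not offered, with reason; or not screened. This is extra site work. Because a documented ineligible patient counts as approached, a site could score well by declaring patients ineligible, so the reason must be recorded and the ineligible share checked.
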